15.1 Definitions of Adverse Events

The following definitions have been adapted from Directive 2001/20/EC, ICH E2A "Clinical Safety Data Management: Definitions and Standards for Expedited Reporting" and ICH GCP E6:

Adverse Event (AE)

Any untoward medical occurrence or effect in a patient treated on a trial protocol, which does not necessarily have a causal relationship with a trial treatment. An AE can therefore be any unfavourable and unintended sign (including an abnormal laboratory finding), symptom or disease temporally associated with the use of a trial treatment, whether or not related to that trial treatment.

Adverse Reaction

All untoward and unintended responses to a trial treatment related to any dose administered. A causal relationship between a trial treatment and an adverse event is at least a reasonable possibility, i.e. the relationship cannot be ruled out.

Serious Adverse Event (SAE) or Serious Adverse Reaction

An adverse event or adverse reaction that at any dose:

- Results in death
- Is life threatening (The term "life-threatening" refers to an event in which the patient was at risk of death at the time of the event. It does not refer to an event that hypothetically might have caused death if it were more severe.)
- Requires in-patient hospitalisation or prolongs existing hospitalisation
- Results in persistent or significant or disability/incapacity
- Is a congenital anomaly or birth defect
- Is otherwise medically significant (e.g. important medical events that may not be immediately life-threatening or result in death or hospitalisation but may jeopardise the patient or may require intervention to prevent one of the other outcomes listed above)

Suspected Unexpected Serious Adverse Reaction (SUSAR)

A serious adverse reaction, the nature or severity of which **is not consistent** with the applicable trial treatment information.

15.2 Reporting Procedures

15.2.1 All Adverse Events (AEs)

All adverse events that occur between the signing of informed consent and 36 months after patient completes CRT must be recorded in the patient notes and the trial CRFs. Those meeting the definition of a Serious Adverse Event (SAE) must also be reported to UCL CTC using the trial specific SAE Report The fact that an overdose has occurred must be clearly stated on the SAE Report. Also refer to section 15.2.2 (Serious Adverse Events (SAEs)).

Pre-existing conditions do not qualify as adverse events unless they worsen.

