8.1 Overall study structure

This is a multi-site phase II enrolment study. Centres participating in the study will include the four North West centres in the NWCOG, plus up to four others.

THE PRIMARY ENDPOINT is the histologically confirmed R0 resection rate.

THE SECONDARY ENDPOINTS are as follows:

- Radiotherapy compliance.
- Grade 3 or 4 toxicity.
- Pathological complete response
- Morbidity post operative and long term.
- Disease-free survival and local failure-free survival.

Patients will be assessed for eligibility prior to recruitment (see inclusion/exclusion criteria).

Treatment should be started as soon as possible after registration. The MRI scan that has been used for eligibility and disease evaluation needs to be within 35 days of registration. Patients should have an acceptable haematological and biochemical profile within 7 days of the first day of chemotherapy administration.

If blood tests and calculated GFR used to confirm eligibility are not within 7 days of treatment start, further testing will be required (see Section 9 for details). If the following were not included in routine investigations prior to registration, they too need to be obtained prior to the start of study treatment as part of the required baseline investigations: CEA, serum magnesium, clotting (see Section 9)

A calculated glomerular filtration rate (GFR) using the Cockroft Formula is acceptable but if this is less than 50 ml/min then a formal 24-hour urine collection or serum EDTA clearance should be carried out to determine GFR (see Appendix 4).

Before CRT begins, 2×10 ml blood samples will be collected from consenting patients. One sample will be used for testing for UGT1A1 polymorphisms and the other will be stored for future research studies (see Section 19). Patients will receive a six week (in total) course of treatment: week 1, cetuximab only; weeks 2 - 6 radiotherapy combined with cetuximab, irinotecan and capecitabine.

A defunctioning stoma will be fashioned for severe symptoms due to the primary tumour at the discretion of the treating team.

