A clinical evaluation will be carried out (doctor/nurse) at the commencement of cetuximab, every week during radiotherapy and for four weeks following completion of treatment to record blood count, biochemical profile, estimated GFR, and toxicity scores (using NCI CTC V.3.0). Serum magnesium is to be monitored weekly for 8 weeks post completion of cetuximab treatment. In patients on anticoagulants or those with an abnormal initial clotting profile, clotting profile is measured weekly during chemotherapy then weekly for four weeks post-termination (and longer if deemed clinically appropriate) if this is abnormal.

An MRI scan will be carried out at six weeks following radiotherapy completion then an attempt at surgery will take place eight weeks post radiotherapy completion.

Following surgery, adjuvant chemotherapy is given according to the discretion of the treating physician but recorded on the relevant CRF.

A sample of formalin-fixed paraffin-embedded tumour tissue removed during surgery will be sent to a central lab for analysis of KRAS mutation status. The tumour tissue will be stored and used in future research studies if the patient has consented to this. Otherwise, it will be returned to the site.

From the point of view of late toxicity, patients will be assessed at 6, 12, 24 and 36 months post completion of radiotherapy.

On confirmed tumour progression further formal follow-up within the trial ceases apart from ultimately recording date and cause of death. Further clinical management, including second-line chemotherapy is at the discretion of the treating physician. On study withdrawal for any reason then the CRF Off Study Form is completed, providing reason for treatment withdrawl and/or complete withdrawl. On patient death, CRF Death Form is (also) completed.

No other concomitant cytotoxic treatment or radiotherapy is permitted during the trial.

Specified dose limiting toxicities:

All toxicities below must adhere strictly to definitions specified in the National Cancer Institute Common Terminology Criteria for Adverse Events v3.0:

 Grade 3 diarrhoea that does not improve to grade 2 or less, within 24 hours on intensive anti-diarrhoeal therapy

- o Grade 4 diarrhoea
- Grade 3 or 4 fatigue
- Grade 3 or 4 neutropenia accompanied by fever (>38°C) or ≥grade 3 infection
- Grade 4 thrombocytopenia (platelet count < 25×10^{9} /L)
- o Grade 4 nausea/vomiting despite full antiemetic treatment

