9.2 Efficacy endpoints

Resectability will be defined in terms of:

- R0 resection rate i.e. the carcinoma is resected with margins clear by >1mm.
- R1 resection rate i.e. the carcinoma has microscopically-involved margins
- R2 resection rate i.e. the carcinoma is resected but has macroscopically-involved margins at the time of surgery.

Response rate will be defined in terms of:

• Pathological complete response (pCR) i.e. no residual viable carcinoma on extensive examination of the resected specimen.

The following will also be recorded:

- 'Near' pCR i.e. microscopic foci of occasional single carcinoma cells remaining on extensive examination of the specimen.
- Decrease in size of the carcinoma in superior-inferior and transaxial dimensions on comparing pre- and post- CRT MRI scans.
- Change in MRI-defined TNM stage of tumour on pre- and post-CRT MRI scans.
- TNM stage of resected specimen compared to predicted on pre-CRT MRI scan.

The denominator will be total numbers of subjects recruited for the trial and commencing CRT treatment.

The following categories of patient will be distinguished:

- Patients undergoing CRT and an attempt at laparotomy but tumour not resected because found to be too locally advanced at surgery.
- Patients undergoing CRT and an attempt at laparotomy but tumour not resected because found to have developed metastatic disease.
- Patients undergoing CRT and an attempt at laparotomy but tumour not resected because of other reasons.
- Patients undergoing CRT but not undergoing surgery because tumour remains too locally-advanced on restaging MRI.

Disease free survival - the 'event' will be time from randomisation to confirmation of local failure or recurrence, distant metastases, or death from any cause, whichever occurs first, disease-free patients being censored at the date last seen.

Local failure – A local failure is defined as:

- pelvic disease extent is considered unresectable (after pre-op CRT has been given and reassessment has taken place).
- when at laparotomy there is residual macroscopic pelvic malignancy.
- when during the follow up period (after macroscopic clearance of tumour was achieved) there is evidence of confirmed local recurrence. Confirmed local recurrence includes biopsy confirmation of local recurrence, unequivocal local recurrence on imaging (MRI scanning and /or PET) or equivocal local recurrence on imaging in the definite absence of metastatic disease and in the presence of a rising CEA.

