10.1 Withdrawal from Trial Treatment

A patient may stop trial treatment for the following reasons:

- Progression whilst on therapy
- o Unacceptable toxicity
- o Intercurrent illness which prevents further treatment
- o Withdrawal of consent for treatment by patient
- Any alterations in the patient's condition which justifies the discontinuation of treatment in the investigator's opinion.

The reason should be recorded on the Treatment CRF and Withdrawal form.

The patient should however remain in the trial for the purposes of follow-up and data analysis, therefore, patients who withdraw from trial treatment for any reason other than disease progression and withdrawal of consent from trial including data collection, will continue to be followed-up for disease progression and late toxicity.

On confirmed tumour progression, further formal follow-up within the trial ceases apart from ultimately recording date and cause of death of death.

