15.2.2 Serious Adverse Events (SAEs)

All SAEs that occur between the signing of informed consent and 30 days post the last trial treatment administration (or after this date if the site investigator feels the event is related to the trial treatment) must be submitted to UCL CTC by fax within **1 business day** of observing or learning of the event, using the trial specific SAE Report. All sections on the SAE Report must be completed. If the event is not being reported within 1 business day to UCL CTC, the circumstances that led to this must be detailed in the SAE report to avoid unnecessary queries.

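### Adverse-event recording has two conflicting end points: 36 months after CRT in 15.2.1, and confirmed tumour progression in 8.1 and 10.1

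*Protocol*

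**What the plan says.** Long-term morbidity is a secondary endpoint in Protocol 1.1 and again in 8.1 ("Morbidity post operative and long term").

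Some provisions run to 36 months and do not mention progression:
- 15.2.1 sets the recording window for the notes and the CRFs: "All adverse events that occur between the signing of informed consent and 36 months after patient completes CRT must be recorded".
- 8.1, on late toxicity: "patients will be assessed at 6, 12, 24 and 36 months post completion of radiotherapy".
- 9.1.5 and Figure 11 schedule late-toxicity assessment and a follow-up CRF at the same four times.

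Others stop earlier:
- 8.1: "On confirmed tumour progression further formal follow-up within the trial ceases apart from ultimately recording date and cause of death".
- 10.1 repeats the rule: "On confirmed tumour progression, further formal follow-up within the trial ceases apart from ultimately recording date and cause of death".
- 10.1 continues late-toxicity follow-up after treatment is stopped only for "patients who withdraw from trial treatment for any reason other than disease progression" or full withdrawal of consent.

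Two further provisions bear on the consequence. In 15.2.2, SAE reporting runs to 30 days after the last treatment, "or after this date if the site investigator feels the event is related to the trial treatment". In 9.2 a denominator is given ("The denominator will be total numbers of subjects recruited for the trial and commencing CRT treatment"), but under the efficacy endpoints. The protocol names no denominator or censoring rule for morbidity.

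**The concern.** The two rules decide which data sites collect. Take a patient whose disease progresses 9 months after CRT. Under 15.2.1 the site owes 36 − 9 = 27 more months of adverse-event recording. Under 8.1 and 10.1 it owes only the details of death. Section 16.1 requires every protocol deviation to be notified, and in this case either course departs from one section.

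Sites may reasonably choose differently. The long-term morbidity data would then combine full 36-month observation for some progressed patients with truncated observation for others, by local reading of the protocol. An analysis plan cannot repair this, because data that were never collected cannot be recovered. Even if every site applied the progression stop, a figure presented as a 36-month rate for all treated patients would describe something narrower.

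**Working it through.** **Do the rules conflict?** Three groups of patients can be separated.
- Progression-free to 36 months: the rules agree.
- Progression before 36 months: 15.2.1 requires recording to continue, while 8.1 and 10.1 end formal follow-up. No section ranks one rule above the other, and 15.2.1 does not refer to 8.1 or 10.1.
- Treatment stopped for progression: 10.1 also takes these patients out of late-toxicity follow-up, while 15.2.1 still covers them.

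**Inputs for the illustration.** The protocol states no progression rate, late-toxicity rate or precision target, so there is no figure of its own to reproduce. The sample size of 80 is from section 13. Everything else is assumed: constant hazards over 36 months, toxicity independent of progression, and no deaths.

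**Crude proportion under the progression stop.** Let P be the 36-month progression risk and M the true 36-month late-toxicity risk. With 36 months as one unit of time, a = −ln(1 − M) and b = −ln(1 − P). The expected proportion of all patients with toxicity recorded before progression is

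a/(a + b) × [1 − exp(−(a + b))].

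For P = 0.35 and M = 0.20:
- a = −ln(0.80) = 0.2231 and b = −ln(0.65) = 0.4308, so a + b = 0.6539.
- exp(−0.6539) = 0.80 × 0.65 = 0.52.
- Recorded proportion = (0.2231/0.6539) × 0.48 = 0.164.
- Shortfall = 20.0 − 16.4 = 3.6 percentage points.
- Standard error of a 20% proportion in 80 patients = √(0.2 × 0.8/80) = 0.045, so the shortfall is about 0.8 standard errors.

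Over a range of assumed rates, the crude recorded percentage is:

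| Progression by 36 months | True risk 10% | True risk 20% | True risk 30% |
|---|---|---|---|
| 10% | 9.5 | 19.0 | 28.6 |
| 20% | 9.0 | 18.0 | 27.1 |
| 30% | 8.4 | 16.9 | 25.5 |
| 40% | 7.9 | 15.8 | 23.8 |
| 50% | 7.3 | 14.6 | 22.1 |

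The shortfall runs from about 0.5 to about 8 points. In the 20% column, 15.2 down to 11.7 patients are recorded with toxicity, against 16 under full recording. The direction does not depend on the model: with the denominator fixed at all treated patients, leaving out events can only lower the proportion or leave it unchanged.

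**Estimate censored at progression.** In the same model a time-to-event estimate that censors at progression returns the true 20%. The table below, from a simulation, lets the toxicity hazard change after progression (30% progression; 20% risk if the hazard is unchanged).

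| Hazard after progression | Full recording | Censored at progression | Crude under the stop |
|---|---|---|---|
| Halved | 18.5% | 20% | 16.9% |
| Unchanged | 20% | 20% | 16.9% |
| Doubled | 22.6% | 20% | 16.9% |

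The censored estimate can therefore be too high, correct or too low. The crude proportion is low in all three rows.

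**Progression as a competing event.** The formula above is also the cumulative incidence of toxicity with progression as a competing event. Reporting that quantity gives the same 16.4%. It is a valid measure of toxicity observed before progression, but it does not estimate the 20%.

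**The case against.** The best defence is that the protocol can be read as intending the stop. In 8.1 the paragraph ending follow-up at progression comes straight after the late-toxicity schedule and reads naturally as its exception. Section 10.1 deals expressly with late toxicity and leaves out patients who stop for progression. On that reading only the general pharmacovigilance sentence in 15.2.1 is out of line. Stopping at progression is also a defensible choice, since 8.1 leaves later management to the physician and later events may reflect disease or subsequent treatment. This narrows the conflict but does not remove it. Section 15.2.1 is mandatory, covers all adverse events and has no exception, and 9.1.5 and Figure 11 are silent.

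A reader might draw four stronger conclusions, which the document does not support:
- **That the long-term morbidity rate is understated.** This follows for a crude proportion over all treated patients, but the protocol fixes no estimator for morbidity, and a censored estimate can err either way or not at all.
- **That every progressed patient counts as free of late toxicity.** Events recorded before progression still count, and the formula includes them.
- **That serious late harm is lost.** Under 15.2.2, SAEs that the investigator considers related stay reportable with no progression cut-off. Non-serious late toxicity has no such route.
- **That the phase III decision is misled.** Section 13 ties that decision to the R0 resection rate, and its stopping guideline concerns grade 3 or 4 diarrhoea.

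Nor do 8.1 and 10.1 prohibit recording after progression; they say that formal follow-up ceases. The illustration also ignores death. Patients who die after progression contribute no later toxicity under either rule, so the recoverable shortfall would be smaller than shown.

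**Conclusion.** The contradiction stands in the current text and affects every patient who progresses before 36 months. It leaves the data for a named secondary endpoint dependent on which section a site follows. The primary R0 analysis is not affected.

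The bias is conditional. It arises if the progression stop is applied and morbidity is summarised as a crude proportion of all treated patients. It is then 3.6 points in the central illustration and roughly 0.5 to 8 points over the range examined. Those sizes rest entirely on assumed rates, constant and independent hazards, and no deaths. The need to reconcile the sections rests on none of these assumptions.

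**What to change.** Set one adverse-event and late-toxicity window and state it identically in 8.1, 9.1.5, 10.1, 15.2.1 and Figure 11. Either option below resolves the conflict.

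1. **Record to 36 months regardless of progression.** Limit the stop in 8.1 and 10.1 to disease assessments, continue the adverse-event and late-toxicity forms, and flag the start of any post-progression treatment. Report late toxicity as cumulative incidence with death as a competing event. The cost is a wording amendment and up to four late-toxicity forms per progressed patient, who is already followed for death. The drawback is that later events are confounded by disease and subsequent treatment, hence the flag.
2. **Stop at progression.** Write the exception into every section listed, including 15.2.1, and keep the 15.2.2 route for related SAEs. Report the result explicitly as toxicity observed before progression, not as a 36-month morbidity rate for all patients. The cost is wording only. The drawback is that toxicity after progression remains unknown, apart from related SAEs.

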15.2.1.1 Overdoses

All accidental or intentional overdoses, whether or not they result in adverse events, must be recorded in the patient notes and CRFs. Overdoses resulting in an adverse event are classified as SAEs and must also be reported to UCL CTC according to SAE reporting procedures. Also refer to section 15.2.2 (Serious Adverse Events (SAEs)).

Sites must inform UCL CTC immediately when an overdose has been identified. Refer to section 16 (Incident Reporting and Serious Breaches).

15.2.1.2 Adverse Event Term

An adverse event term needs to be provided for each adverse event, preferably using the Short Name as listed in the Common Terminology Criteria for Adverse Events (CTCAE) v3.0, available online at:

http://ctep.cancer.gov/protocolDevelopment/electronic_applications/docs/ctcaev3.pdf

15.2.1.3 Severity

Severity for each adverse event must be determined by using the Common Terminology Criteria for Adverse Events (CTCAE) v3.0 as a guideline, wherever possible. The criteria are available online at:

http://ctep.cancer.gov/protocolDevelopment/electronic_applications/docs/ctcaev3.pdf In those cases where the CTCAE criteria do not apply, severity should be coded according to the following criteria:

- 1 = Mild (aware of sign or symptom, but easily tolerated)
- 2 = Moderate (discomfort enough to cause interference with normal daily activities)
- 3 = Severe (inability to perform normal daily activities)
- 4 = Life threatening (immediate risk of death from the reaction as it occurred)
- 5 = Fatal (the event results in death)

15.2.1.4 Causality

The PI, or other delegated site investigator, must perform an evaluation of causality for each adverse event. Causal relationship to each trial treatment must be determined as follows:

• None

There is no evidence of any causal relationship.

• Unlikely

There is little evidence to suggest a causal relationship (e.g. because the event did not occur within a reasonable time after administration of a trial treatment). There is another reasonable explanation of the event (e.g. the patient's clinical condition, other concomitant treatments).

Possibly

There is some evidence to suggest a causal relationship (e.g. because the event occurs within a reasonable time after administration of a trial treatment). However, the influence of other factors may have contributed to the event (e.g. the patient's clinical condition, other concomitant treatments).

Probably

There is evidence to suggest a causal relationship and the influence of other factors is unlikely.

• Definitely

There is clear evidence to suggest a causal relationship and other possible contributing factors can be ruled out.

15.2.2 Serious Adverse Events (SAEs)

All SAEs that occur between the signing of informed consent and 30 days post the last trial treatment administration (or after this date if the site investigator feels the event is related to the trial treatment) must be submitted to UCL CTC by fax within **1 business day** of observing or learning of the event, using the trial specific SAE Report. All sections on the SAE Report must be completed. If the event is not being reported within 1 business day to UCL CTC, the circumstances that led to this must be detailed in the SAE report to avoid unnecessary queries.

15.2.2.1 Exemptions from SAE Report Submission

[figure not shown]
For this trial, the following events are exempt from requiring submission on an SAE Report, but must be recorded in the relevant section(s) of the trial CRF:

• disease progression (including disease related deaths)

Please note that hospitalisation for elective treatment or palliative care does not qualify as an SAE.

Completed SAE Reports must be faxed within 1 business day of becoming aware of the event to UCL CTC [contact]

